#### **10.1.13 Treatment Cycles 3+ Visits**

Subjects with an ongoing response of at least SD subsequent to the end of cycle 2 will be offered continued treatment with MOR03087 until disease progression or death or start of new anti-myeloma treatment.

At the discretion of the investigator, subjects with disease progression or a status no better than stable disease after four cycles may be treated with up to 40 mg DEX (elderly subjects aged > 75 years should receive 20 mg) per week if not otherwise receiving DEX via assigned cohort. Only subjects who do not present with known or suspected hypersensitivity to DEX or any of the excipients could qualify for the treatment with DEX (see exclusion criterion for the concomitant treatment of MOR03087 and DEX, Section 8.2). DEX must be administered as a single oral dose.

In case subjects are treated with DEX in the course of the study, the investigator may decide to decrease the dose of DEX when medically justified in the light of signs and symptoms resulting from the excess of glucocorticosteroids. The investigator must then adhere to the rules of local medical practice and their clinical judgment in the process, ensuring that subject treatment is stable (down-titration completed) prior to the End of Study (EOS) visit.

In case a subject discontinues treatment for reasons other than disease progression, they should proceed to the Follow-up Visit.

All subjects (females as well as males) continuing in the LEN and POM parts will receive an educational leaflet appropriate to their treatment, and will receive Pregnancy Counselling (see Section 12.2 and Appendix 18.8.1.3 / 18.8.2.3) at Day 1 of each cycle, starting with Cycle 3+.

At each ongoing treatment visit, the following will be obtained, performed, or assessed prior to study drug administration:

- Toxicity/AE assessment since the last visit
- Concomitant medication
- Karnofsky performance status only at Day 1 (CxD1) of each cycle, starting with Cycle 3+
- Laboratory assessments according to local guidelines/practice for the administration of monoclonal antibodies at the local laboratory should be performed. The assessment at the local laboratory should contain at the minimum serum chemistry including the "emergency laboratory parameters" and calcium concentration, and hematology
- Urine pregnancy test for women of child-bearing potential only at Day 1 (CxD1) of each cycle, starting with Cycle 3+
- Serum M-protein and serum free light chains only at Day 1 (CxD1) of each cycle, starting with Cycle 3+
- Sample from 24-hour urine for urine M-protein only at Day 1 (CxD1) of each cycle, starting with Cycle 3+
- B, T and NK cells at Day 15 (CxD15) of each cycle, starting with Cycle 3+
- Blood sample for predose pharmacokinetics (MOR03087) and anti-MOR03087 antibodies every CxD15
- Response assessment on Day 1 of every cycle (CxD1), to be continued until disease progression or death or subsequent anti MM therapy start whatever occurs first. Note: all responses require two consecutive assessments, and should ideally be confirmed at Day 1 of the next cycle

- Physical examination (including basic neurological examination of general motor and sensory systems, mental status, cranial nerves, and coordination)
- Body weight
- Vital signs (blood pressure, pulse rate, respiratory rate, and body temperature immediately before infusion)
- Premedication (at the investigator's discretion if no infusion reaction during Cycle 1)

For subjects receiving POM or LEN, the additional following will be obtained, performed, or assessed prior to study drug administration:

- 12-lead ECG
  - For subjects treated in Part D (POM), 12-lead ECG monitoring will be performed on Cycle 3 Day 1, and on Day 1 of every third cycle thereafter (Cycles 3, 6, 9, etc.), and at treatment discontinuation. Subjects with QT prolongation (or borderline QT prolongation) but otherwise non-clinically significant will require more frequent ECG monitoring at the discretion of the investigator.
  - For subjects treated in Part E (LEN), 12-lead ECG will be performed at each visit during treatment if clinically indicated per investigator's judgment, and at treatment discontinuation if clinically indicated per investigator's judgment
- Clinical review of signs/symptoms for possible VTEs in subjects treated with POM or LEN. Subjects who develop symptomatic deep vein thrombosis will be assessed and diagnosed objectively by Doppler ultrasonography or a comparable method per institution's standard of care. See Appendix 18.9 for deep vein thrombosis and pulmonary embolism diagnostic algorithms
- Prophylactic treatment of thromboembolism for subjects enrolled into the LEN or POM cohorts

Study drug administration:

- MOR03087 study drug administration
- DEX, POM, LEN administration according to cohort assignment; POM and LEN will be administered daily on Days 1-21 of each 28-day cycle; time point for oral application of POM or LEN at start of MOR03087 infusion (+/- 5min). DEX should be given up to 3 hours prior to MOR03087 infusion start.

The following will be obtained, performed, or assessed after start of study drug administration:

- Vital signs (blood pressure, pulse rate, respiratory rate, and body temperature) at end of infusion
- Blood sample for pharmacokinetics (MOR03087; after completion of infusion but only every CxD15
- Ongoing toxicity/AE assessment during the visit

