#### Table 2 Flow Chart and Schedule of Assessments: Parts B-E (Weekly/Biweekly Administration)

¹A Follow-up visit will be repeated every fourth week (± 2 days) until progressive disease, or receipt of new anti-myeloma treatment, or until death, but no longer than 3 years from the first study drug administration. Follow-up visits may be delayed for a maximum of 2 weeks after the normal visit window due to other reasons (e.g., logistical).

² The EOS visit will occur after at least 28 days after last study drug administration but should be performed before any new MM therapy starts, whichever occurs first. Subjects who complete Cycle 2 but do not receive additional cycles (Cycle 3+), have to perform Follow-up visit 1 and Follow-up visit 2 before EOS visit.

³ Including disease staging based on Durie-Salmon and International Staging System (ISS) criteria and documentation of immunoglobulin type.

⁴ Before study drug administration.

⁵ Each cycle, starting with Cycle 3+: pre-dose at Day 1 (CxD1)

⁶ During Cycle 1, all subjects should be given premedication including an antipyretic (e.g., paracetamol) and a histamine H1 receptor blocker according to the local standard of care. In medically justified cases, the investigator may use other medications (e.g., steroids for the non-DEX cohorts) as per local standard but not exceeding 10 mg prednisolone equivalent), doses

Sponsor: MorphoSys AG

Confidential

Product Name: MOR03087 Date: 17 Jul 2017 Protocol Amendment 11, Final 12.0 Protocol Number: MOR202C101 EudraCT Number: 2009-015942-50

and/or formulations if this is documented thoroughly in the eCRF and the source data. If no infusion reaction occurs during Cycle 1, then premedication can be stopped at investigator's discretion of the investigator for subsequent treatment cycles. Otherwise, the premedication should be continued for subsequent administrations of MOR03087 as well.

⁷ DEX should be given up to 3 hours prior to MOR03087 infusion start.

⁸ Subjects in Parts D and E are to take POM or LEN capsules, respectively, on Days 1-21 of each treatment 28-day cycle. Thromboembolism prophylaxis during the study treatment is required for subjects; low-dose aspirin, low molecular weight heparin, or other equivalent antithrombotic or anti-coagulant will be given to all subjects taking POM or LEN; Oral application of POM or LEN must be performed at start of MOR03087 infusion (+/- 5min)

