⁹ Emergency Laboratory only to be taken if hematology/serum chemistry is not available prior to study drug administration

¹⁰ Sample to be taken and evaluated before study drug administration. On Day 1, additional sample (except AST and ALT) to be taken 2 hours after end of infusion.

¹¹ β2-microglobulin to be measured at Screening only.

¹² For subjects treated with POM or LEN (Parts D or E), the first pregnancy test must be performed within 10-14 days prior to the start of study treatment, and a second pregnancy test must be performed within 24 hours prior to the start of study treatment.

¹³ For female subjects with irregular cycles treated in Parts D and E (POM and LEN), an additional pregnancy test is required 14 days after treatment discontinuation.

¹⁴ Subjects treated in Parts D and E only (POM and LEN): Serum or urine pregnancy test must be performed.

¹⁵Pharmacokinetic sample (MOR03087) to be taken predose and then at 1, 2, 4, 8, 14±2 (optional), 22±2, and 28±2 hours after start of first MOR03087 infusion.

¹⁶ Pharmacokinetic sample (MOR03087, LEN or POM) to be taken predose and after completion of MOR03087 infusion.

¹⁷ Pharmacokinetic sample during treatment cycles 3+ to be taken every CxD15 predose and after completion of infusion.

¹⁸ Only if subject had no follow-up visit.

¹⁹ Pharmacokinetic sample (POM or LEN) to be taken predose before administration of MOR03087 + LEN or POM and then at 1, 2, 8, 22±2 hours after start of first MOR03087 infusion.

²⁰ Samples for anti-MOR03087 antibodies will also be used to determine tetanus titer if sufficient quantities of serum available.

²¹ Anti-MOR03087 antibody sample during treatment Cycles 3+ to be taken every CxD15 predose.

²² At second follow-up visit only.

²³ Including CD16 expression on NK cells.

²⁴ Each cycle, starting with Cycle 3+: pre-dose at Day 15 (CxD15)

²⁵ For urine M-protein evaluation, 24-hour urine has to be collected. During the first two cycles more Serum and urine M-protein, serum free light chains will be collected.

²⁶ For urine M-protein evaluation at Screening, use of pre-collected 24h urine sample which MM subjects bring to the hospital for every routine visit within the scope of usual standard of care procedure is accepted.

²⁷ Evaluation on Day 1 of every cycle (CxD1). All response categories require two consecutive assessments made at any time prior to the start of any new therapy.

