- Concomitant medications
- Blood sample for "emergency laboratory" for immediate evaluation before study drug administration (only to be taken if hematology/serum chemistry is not available prior to study drug administration), hematology, serum chemistry, anti-MOR03087 antibodies, and predose pharmacokinetics (MOR03087), serum M-Protein and serum FLC assessments.
- Sample from 24-hour urine for M-Protein
- Physical examination (including basic neurological examination of general motor and sensory systems, mental status, cranial nerves, and coordination)
- Body weight
- Quality of life questionnaires (QLQ-MY20 and QLQ-C30)
- Vital signs (blood pressure, pulse rate, respiratory rate, and body temperature)
- Premedication

For subjects receiving weekly treatment, the additional following will be obtained, performed, or assessed prior to study drug administration:

- Clinical review of signs/symptoms for possible VTEs in subjects treated with POM or LEN. Subjects who develop symptomatic deep vein thrombosis will be assessed and diagnosed objectively by Doppler ultrasonography or a comparable method per institution's standard of care. See Appendix 18.9 for deep vein thrombosis and pulmonary embolism diagnostic algorithms
- Prophylactic treatment of thromboembolism for subjects enrolled into the LEN or POM cohorts
- For subjects treated with LEN, 12-lead ECG may be performed at the investigator's discretion
- For women of childbearing potential in study cohorts that include LEN or POM, a pregnancy test (serum or urine) is to be performed

Study drug administration:

- MOR03087 Study drug administration
- DEX, POM, LEN administration according to cohort assignment; POM and LEN will be administered daily on Days 1-21 of each 28-day cycle; time point for oral application of

POM or LEN at start of MOR03087 infusion (+/- 5min). DEX should be given up to 3 hours prior to MOR03087 infusion start.

The following will be obtained, performed, or assessed after start of study drug administration:

- Vital signs (blood pressure, pulse rate, respiratory rate, and body temperature) at 15 minutes, 30 minutes, and 1 hour after start of infusion; end of infusion; and 2 and 4 hours after end of infusion
- Blood sample for MOR03087 pharmacokinetics (after completion of infusion)
- Ongoing toxicity/AE assessment during the visit

# 10.1.7 Cycle 1: Day 22

On Day 22, the following will be obtained, performed, or assessed (for weekly treatment prior to study drug administration):

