### 10.1.10 Day 43 Visit (C2D15)

The MOR03087 vial(s) have to be obtained from the freezer 3 days to 16 hours before planned start of study drug administration. The vials have to be thawed and stored at 2-8°C until preparation for administration.

The following will be obtained, performed, or assessed prior to study drug administration:

- Toxicity/AE assessment since the last visit
- Concomitant medication
- Karnofsky performance status
- Blood sample for "emergency laboratory" for immediate evaluation before study drug administration (only to be taken if hematology/serum chemistry is not available prior to study drug administration), hematology, serum chemistry, endocrinology, anti-MOR03087 antibodies, serum M-protein, serum FLCs, and predose pharmacokinetics (MOR03087)
- Sample from 24-hour urine for urine M-protein
- Physical examination (including basic neurological examination of general motor and sensory systems, mental status, cranial nerves, and coordination)
- Body weight
- Quality of life questionnaires (QLQ-MY20 and QLQ-C30)
- Vital signs (blood pressure, pulse rate, respiratory rate, and body temperature)
- Premedication (at the investigator's discretion if no infusion reaction during Cycle 1)

For subjects receiving weekly treatment, the additional following will be obtained, performed, or assessed prior to study drug administration:

- Blood sample for predose pharmacokinetics (LEN / POM)
- Clinical review of signs/symptoms for possible VTEs in subjects treated with POM or LEN. Subjects who develop symptomatic deep vein thrombosis will be assessed and diagnosed objectively by Doppler ultrasonography or a comparable method per institution's standard of care. See Appendix 18.9 for deep vein thrombosis and pulmonary embolism diagnostic algorithms
- Prophylactic treatment of thromboembolism for subjects enrolled into the LEN or POM cohorts
- For subjects treated with LEN, 12-lead ECG may be performed at the investigator's discretion

Study drug administration:

- MOR03087 Study drug administration
- DEX, POM, LEN administration according to cohort assignment; POM and LEN will be administered daily on Days 1-21 of each 28-day cycle; time point for oral application of POM or LEN at start of MOR03087 infusion (+/- 5min). DEX should be given up to 3 hours prior to MOR03087 infusion start.

The following will be obtained, performed, or assessed after start of study drug administration:

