**Pregnancy Counseling (males and females):** Counseling about pregnancy precautions and the potential risks of fetal exposure must be conducted for all subjects at screening, at Cycle 1 Day 1 prior to dosing, every 28 days during treatment, and at treatment discontinuation. Refer to Appendix 18.8 (pregnancy prevention risk minimization plan).

**Pregnancy Testing for Females of Childbearing Potential (FCBP):** All FCBP must have two medically supervised negative serum or urine pregnancy tests (sensitivity of at least 25 mIU/mL) prior to starting the study. The first pregnancy test must be performed within 10-14 days prior to the start of study treatment and the second pregnancy test must be performed within 24 hours prior to the start of study treatment. FCBP with regular or no menstrual cycles must agree to have pregnancy tests every 7 days (weekly) for the first 4 weeks of study treatment and then every 4 weeks while on study, at treatment discontinuation, and 4 weeks following treatment discontinuation. If menstrual cycles are irregular, the pregnancy testing must occur weekly for the first 4 weeks and then every 2 weeks while on study, at treatment discontinuation. Study drug may not be dispensed for FCBP until the investigator has verified that the result of the pregnancy test is negative.

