## During study participation and for 28 days following study drug discontinuation

## Female Subjects:

- FCBP with regular or no menstrual cycles must agree to have pregnancy tests weekly for the first 28 days of study participation and then every 28 days while on study, at study discontinuation, and at day 28 following study drug discontinuation. If menstrual cycles are irregular, the pregnancy testing must occur weekly for the first 28 days and then every 14 days while on study, at study discontinuation, and at days 14 and 28 following study drug discontinuation.
- At each visit, the Investigator must confirm with the FCBP that she is continuing to use two reliable methods of birth control.
- Counseling about pregnancy precautions and the potential risks of fetal exposure must be conducted at a minimum of every 28 days.
- If pregnancy or a positive pregnancy test does occur in a study subject, study drug must be immediately discontinued.

- Pregnancy testing and counseling must be performed if a subject misses her period or if her pregnancy test or her menstrual bleeding is abnormal. Study drug treatment must be discontinued during this evaluation.
- Females must agree to abstain from breastfeeding during study participation and for at least 28 days after study drug discontinuation.

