## During study participation and for 28 days following study drug discontinuation

## Female Subjects:

- FCBP with regular or no menstrual cycles must agree to have pregnancy tests weekly for the first 28 days of study participation and then every 28 days while on study, at study discontinuation, and at day 28 following study drug discontinuation. If menstrual cycles are irregular, the pregnancy testing must occur weekly for the first 28 days and then every 14 days while on study, at study discontinuation, and at days 14 and 28 following study drug discontinuation.
- At each visit, the Investigator must confirm with the FCBP that she is continuing to use two reliable methods of birth control.
- Counselling about pregnancy precautions and the potential risks of fetal exposure must be conducted at a minimum of every 28 days.
- If pregnancy or a positive pregnancy test does occur in a study subject, study drug must be immediately discontinued.

- Pregnancy testing and counselling must be performed if a subject misses her period or if her pregnancy test or her menstrual bleeding is abnormal. Study drug treatment must be discontinued during this evaluation.
- Females must agree to abstain from breastfeeding during study participation and for at least 28 days after study drug discontinuation.

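### From Cycle 2 the visit schedule lists one pregnancy test per 28-day cycle, but women with irregular menstrual cycles on lenalidomide or pomalidomide must be tested every 14 days

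*Protocol*

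**What the plan says.** **The rule.** For cohorts receiving POM or LEN, Section 12.2 states: "If menstrual cycles are irregular, the pregnancy testing must occur weekly for the first 4 weeks and then every 2 weeks while on study". The LEN plan (Appendix 18.8.1.2) says that in women with irregular cycles "the pregnancy testing must occur weekly for the first 28 days and then every 14 days while on study". The POM plan (Appendix 18.8.2.2) says the same: "If menstrual cycles are irregular, the pregnancy testing must occur weekly for the first 28 days and then every 14 days while on study". Women with regular or no cycles need a test every four weeks after the first four.

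**The schedule.**
- The urine pregnancy test row of Table 2 is marked at Days 1, 8, 15, 22 and 29, and then in the Cycles 3+ column. It is blank at Day 43 (Cycle 2 Day 15). Footnote 5 governs the Cycles 3+ cell: "Each cycle, starting with Cycle 3+: pre-dose at Day 1 (CxD1").
- Section 10.1.8 (Cycle 2 Day 1) includes a test.
- Section 10.1.10 (Cycle 2 Day 15) has a list of additions for weekly treatment, including "Blood sample for predose pharmacokinetics (LEN / POM"), but no pregnancy test.
- Section 10.1.13 sets the test for Cycles 3 and later as "Urine pregnancy test for women of child-bearing potential only at Day 1 (CxD1) of each cycle, starting with Cycle 3". Its separate list for POM or LEN subjects adds ECG, thrombosis review and thromboprophylaxis, but no pregnancy test.

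**Irregular cycles in the schedule.** They appear only after treatment stops. Footnote 13 of Table 2 reads "For female subjects with irregular cycles treated in Parts D and E (POM and LEN), an additional pregnancy test is required 14 days" after discontinuation, and Section 10.1.12 repeats this.

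**The concern.** A site that works from Table 2 and the visit sections will test a woman with irregular cycles every 28 days. A site that works from Section 12.2 or the risk minimization plan will test her every 14 days. The protocol treats both drugs as possible human teratogens, and a positive test requires immediate discontinuation, so the interval bears on how long a fetus could be exposed.

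The unlisted test falls on Day 15, when LEN or POM is still being taken (Days 1–21). A pregnancy found before dosing that day could spare up to 21 − 15 + 1 = 7 daily doses in that cycle. Under the 28-day schedule it would not be found until the next Day 1.

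Sections 8.2.2 and 8.2.3 make the plans binding, so a site that follows the schedule alone also deviates from the protocol in every cycle.

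**Working it through.** The plan states no figure to reproduce. The check compares the required and scheduled test days for a woman with irregular cycles in Part D or E, then counts them.

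**Inputs**
- Cycle length: 28 days (Section 7.1).
- Required: weekly for four weeks, then every 14 days (Section 12.2; Appendices 18.8.1.2 and 18.8.2.2).
- Scheduled: Cycle 1 Days 1, 8, 15 and 22 (Table 2; Sections 10.1.2 and 10.1.5 to 10.1.7), then Day 1 of each cycle (Table 2 with footnote 5; Sections 10.1.8 and 10.1.13).
- Maximum duration: three years from first treatment (Section 7.1), or 1,095 days. 39 × 28 = 1,092 days, so about 39 cycles.
- Not counted: the screening test, and tests at and after treatment discontinuation.

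**Side by side**

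| Period | Required | Scheduled |
|---|---|---|
| Cycle 1 | Days 1, 8, 15, 22 | Days 1, 8, 15, 22 |
| Cycle 2 | Day 29 and Day 43 | Day 29 |
| Each cycle from 3 | Day 1 and Day 15 | Day 1 |

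**Counts over n cycles**
- Required = 4 + 2(n − 1)
- Scheduled = 4 + (n − 1)
- Unscheduled = n − 1

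| n | Required | Scheduled | Unscheduled | Share |
|---|---|---|---|---|
| 1 | 4 | 4 | 0 | 0% |
| 2 | 6 | 5 | 1 | 1/6 = 16.7% |
| 6 | 14 | 9 | 5 | 5/14 = 35.7% |
| 13 (364 days) | 28 | 16 | 12 | 12/28 = 42.9% |
| 39 (1,092 days) | 80 | 42 | 38 | 38/80 = 47.5% |

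The share rises only because the fully covered first cycle is diluted. The underlying fact is constant: from Cycle 2, one of two required tests per cycle is not scheduled.

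For women with regular or no cycles, required = scheduled = 4 + (n − 1), so nothing is missing.

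**Omission or deliberate delegation to the appendices?** The schedule copies other parts of the pregnancy plan into the visits. Footnote 12 of Table 2 carries the two pre-treatment tests, footnote 14 the extra LEN/POM tests in Cycle 1, and footnote 13 the post-treatment test for irregular cycles. Only the on-treatment rule for irregular cycles was left out, which points to an omission.

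**The case against.** The strongest reply is that the rule is never in doubt.

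- **Signed forms.** The Education and Counselling Guidance Documents (Appendices 18.8.1.3 and 18.8.2.3) state the 14-day interval for irregular cycles. They must be completed and signed before each dispensing, and only one cycle of drug may be dispensed at a time. Site staff therefore meet the correct interval every cycle.
- **Cross-references.** Sections 10.1.8 and 10.1.13 refer LEN and POM subjects to Section 12.2 and the counselling appendices. Sections 8.2.2 and 8.2.3 tell investigators to follow the plans.
- **The word *only*.** Section 10.1.13 uses it in a list for all cohorts, and in the same way for Karnofsky status and M-protein. In context it spares the other visits in the cycle a routine item; it does not forbid an extra test. Section 12.2 also allows urine tests to be repeated, so both instructions can be followed together.
- **Size.** The subgroup is small and could be empty, and few women with relapsed or refractory myeloma would stay on treatment for 39 cycles.

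Much of this stands. The tests are unlisted, not abolished. The safeguards lower the practical risk, and the long-duration counts are upper bounds. It does not remove the conflict: Table 2 and the visit sections still give a different interval, with no on-treatment exception. The forms and cross-references help only a reader who goes beyond the schedule.

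**Conclusion.** The inconsistency is real and should be fixed. From Cycle 2, the schedule gives 28 days between tests where the protocol's own rule for women with irregular cycles on LEN or POM is 14 days.

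The scope is narrow: women of childbearing potential with irregular cycles in Parts D and E. Those parts plan at most 18 + 18 = 36 subjects of both sexes, and the documents do not say how many would be in the subgroup. This is a matter of participant safety and protocol compliance; it changes no endpoint, DLT rule or analysis. The counts assume 28-day cycles without delay.

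**What to change.** 1. In Table 2, mark the urine pregnancy test at Day 43 and at Day 15 of each later cycle. Add a footnote limiting these tests to women of childbearing potential with irregular cycles in Parts D and E, serum or urine, with the result available before dosing.
2. Add the same line to Sections 10.1.10 and 10.1.13. Section 10.1.6 has wording that can be adapted: "For women of childbearing potential in study cohorts that include LEN or POM, a pregnancy test (serum or urine) is to be performed".
3. In Section 10.1.13, delete the word *only* or qualify it with this exception.
4. As a minor alignment, list pregnancy counselling at Cycle 1 Day 1 and at treatment discontinuation in Table 2 and the visit sections, since Section 12.2 asks for both. The form signed before dispensing already largely covers Cycle 1 Day 1.

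The main change costs one footnote and two lines of visit text. The test is already mandatory, and a Day 15 visit exists in every cycle, including on the biweekly schedule from Cycle 4. It adds no visit and no new requirement.
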